## 4.3. JUSTIFICATION FOR DOSE

Control Group:

- In accordance with current AMH guidelines patients randomised to the control arm will be prescribed daily oral iron at a dose of (3-6mg/kg) elemental iron up to 200mg/day maximum.

Treatment Group:

- Those patients randomised to the treatment arm will be prescribed IV ferric carboxymaltose. The appropriate dose will be calculated using the Ganzoni equation (see section 6.1.2) which is a widely accepted method to calculate the patient's total iron deficit.

## 4.4. END OF STUDY DEFINITION

A participant is considered to have completed the study if he or she has completed all investigations of the study including the last visit shown in the Schedule of Activities (SoA), Section 1.3.

The end of the study is defined as completion of the last visit or procedure shown in the SoA in the trial globally.

# 5. STUDY POPULATION

## 5.1. INCLUSION CRITERIA

In order to be eligible to participate in this study, an individual must meet all of the following criteria:

1. Provision of signed and dated informed consent form
2. Stated willingness to comply with all study procedures and availability for the duration of the study
3. Age <18 years
4. Diagnosed with adolescent idiopathic scoliosis

5. Requiring posterior spinal fusion surgery of greater than or equal to 6 vertebral levels or other spinal fusion surgery associated with significant blood loss as determined by the surgical team
6. Ability to take oral medication and be willing to adhere to the oral iron regimen
7. Willingness to attend hospital to undergo intravenous cannulation as required for the intravenous iron regimen
8. Agreement to adhere to Lifestyle Considerations (see section 5.3) throughout study duration

## 5.2. EXCLUSION CRITERIA

An individual who meets any of the following criteria will be excluded from participation in this study:

1. Any patient who is found to not be iron deficient on preoperative screening
2. Any patient who is found to have hypophosphataemia, hyperparathyroidism or low Vitamin D levels on preoperative screening
3. Current use of iron supplements
4. Pregnancy or lactation
5. Known allergic reactions to components of the IV ferric carboxymaltose or oral iron supplements
6. Significant medical co-morbidity such as neuromuscular disease, severe anaemia, cardiac disease, significant respiratory disease or impairment
7. Haematological contraindication to iron therapy such as sickle cell disease or thalassaemia
8. Significant needle phobia

## 5.3. LIFESTYLE CONSIDERATIONS

During this study, participants are asked to:

- Refrain from consumption of multivitamins or oral iron supplementation other than that prescribed in the trial from the time of enrolment until after the final investigations (12 weeks post operatively)
- Take iron supplements at least 2 hours after or 30 minutes before a meal.
- Abstain from tannin-containing products (e.g., coffee, tea, cola drinks, and chocolate) and antacids for 2 hours before taking their oral iron supplementation.

## 5.4. SCREEN FAILURES

Not Applicable

## 5.5. STRATEGIES FOR RECRUITMENT AND RETENTION

Patients routinely present to the preoperative spinal clinic at the Women's and Children's Hospital 6 weeks prior to their planned surgery date. All patients will be screened to determine their eligibility to enrol in this trial and those who meet the inclusion criteria will be approached and consented by a member of the spinal surgery team. Parents will be given information on the role of iron stores in the perioperative period and the treatment options currently available for correction of iron deficiency (see patient information sheet). They will be given an opportunity ask further questions about their participation in the study prior to signing informed consent.

As this trial focuses on the efficacy of iron therapy in the paediatric surgical patient we will be targeting young people under the age of 18 years. Information will be provided to and in addition to parental consent we will seek assent/consent from those children who are able provide such.

## 6. STUDY INTERVENTION

### 6.1. STUDY INTERVENTION(S) ADMINISTRATION

#### 6.1.1. STUDY INTERVENTION DESCRIPTION

##### Intravenous Ferric Carboxymaltose (Ferinject)

Ferinject solution for injection/infusion is a colloidal solution of the iron complex ferric carboxymaltose.

The complex is designed to provide, in a controlled way, utilisable iron for the iron transport and storage proteins in the body (transferrin and ferritin, respectively). Red Cell utilisation of Fe from radio-labelled Feinject ranged from 91% to 99% in subjects with iron deficiency and 61% to 84% in subjects with renal anaemia at 24 days post-dose. Ferinject treatment of patients with iron deficiency anaemia results in an increase in reticulocyte count and serum ferritin levels to within normal ranges.

##### Oral Iron Supplements

In this study 2 forms of oral iron supplements are available

- Ferro-tab oral iron supplements contain 200mg of Ferrous Fumarate (67.5mg of elemental iron) in a film coated tablet. Ferro-Tab tablets also contain croscarmellose sodium, glycerol, macrogel 400 and macrocell 6000, microcrystalline cellulose, sodium laurel sulphate, sodium starch glycol late Type A, magnesium stearate, hypromellose, talc, titanium dioxide and iron oxides (black, red and yellow).
- Ferro-liquid contain ferrous sulfate 150 mg (= elemental iron 30 mg)/5 mL. Ferro-liquid also contains the following excipients: Sucrose, sodium bisulfite, propyl hydroxybenzoate, sorbitol.

#### 6.1.2. DOSING AND ADMINISTRATION

##### IV Ferric Carboxymaltose

The following dosing guidelines are per the product information guide produced by the manufactures of ferric carboxymaltose.

Using the Ganzoni Formula to estimate total iron deficit:

Total iron dose (mg iron) = Weight(kg) x (Target Hb\* - Actual Hb)(g/L) x 0.24 + Iron for stores\*\*

Where:

\* Target Hb <35kg = 130g/L  
>35kg = 150g/L

\*\* Iron for stores <35kg = 15mg/kg  
>35kg = 500mg

The above calculated dose will be administered in the Medical Day Unit according to the CMI and manufactures guidelines.

A single ferric carboxymaltose administration should not exceed 1000mg or 20mg/kg as per the manufactures recommendation. It is advised that those patients requiring larger doses receive their iron replacement in two divided doses administered 1 week apart.

Oral Iron Supplements

Dosing is based on the AMH Children's Dosing Companion Guidelines:

- 1 month - 18 years, oral 3-6 mg/kg (maximum 200 mg) daily of elemental iron

In consultation with the haematology department at the Women's and Children's Hospital the following doses of oral iron are suggested:

1. To increase tolerability and patient compliance, the iron supplementation will be started at half the recommended dose (3mg/kg/day) for 5 days.
2. Once drug tolerance is established (Day 6) the patient are will be instructed to increase to a full dose (6mg/kg/day - maximum 200mg elemental iron) to be taken until the day before surgery.

The following Dose banding has been done to achieve supplementation within 90-110% of the intended dose:

- **Prescribing of oral ferrous sulfate liquid for 12 hourly dosing:**

Ferrous sulfate 6mg/mL elemental iron - 12 hourly dosing		
Patient weight (kg)	Days 1-5 (dose in mL)	Day 6 -until surgery (dose in mL)
10	2.5	5
11	3	5
12	3	6
13	3	6
14	3.5	7
15	3.5	7
16	4	8
17	4	8
18	4.5	9
19	4.5	9
20	5	10
21	5	10
22	5.5	11
23	5.5	11
24	6	12
25	6	12
26	6.5	13

Ferrous sulfate 6mg/mL elemental iron - 12 hourly dosing		
Patient weight (kg)	Days 1-5 (dose in mL)	Day 6 -until surgery (dose in mL)
27	6.5	13
28	7	14
29	7	14
30	7.5	15
31	7.5	15
32 and above	8	16

- **Prescribing of oral ferrous sulfate liquid for 8 hourly dosing:**
  - In patients who experience gastrointestinal side effects (nausea, abdominal pain) it may be beneficial to administer the dose in 3 divided doses (8 hourly).

Ferrous sulfate 6mg/mL elemental iron - 8 hourly dosing		
Patient weight (kg)	Days 1-5 (dose in mL)	Day 6 -until surgery (dose in mL)
10	1.5	3.5
11	2	3.5
12	2	4
13	2	4
14	2.5	5
15	2.5	5
16	2.5	5
17	3	6
18	3	6
19	3	6
20	3.5	7
21	3.5	7
22	3.5	7
23	4	8
24	4	8
25	4	8
26	4.5	9
27	4.5	9

Ferrous sulfate 6mg/mL elemental iron - 8 hourly dosing		
Patient weight (kg)	Days 1-5 (dose in mL)	Day 6 -until surgery (dose in mL)
28	4.5	9
29	5	10
30	5	10
31	5	10
32	5	10
33	5.5	11
34 and above	5.5	11

- **Prescribing of oral ferrous fumarate (not to be used in children <20kg)**

Ferrous Fumarate 67.5mg/tab elemental iron		
Patient weight (kg)	Days 1-5	Day 6 -until surgery
20-27	1 tablet daily	1 tablet twice daily
27-32	1 tablet daily	1 tablet three times daily
33 and above	1 tablet twice daily	1 tablet three times daily

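### The ferrous fumarate table does not meet the Protocol's own 90–110% banding statement at several weights, and it places a 27 kg child in two bands with different doses from Day 6

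*Protocol*

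**What the plan says.** Section 6.1.2 of the Protocol has the oral arm "started at half the recommended dose (3mg/kg/day) for 5 days" and then raised to a "full dose (6mg/kg/day - maximum 200mg elemental iron) to be taken until the day before surgery". It then states: "The following Dose banding has been done to achieve supplementation within 90-110% of the intended dose". Three tables follow that sentence: ferrous sulfate liquid 12-hourly, ferrous sulfate liquid 8-hourly, and ferrous fumarate tablets.

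The tablet table is headed "Ferrous Fumarate 67.5mg/tab elemental iron". Section 6.1.1 gives the same tablet strength. Its three bands are:

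- 20–27 kg: one tablet a day, then two a day from Day 6.
- 27–32 kg: one tablet a day, then "1 tablet three times daily".
- 33 kg and above: two tablets a day, then three a day.

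Section 4.3 says control patients "will be prescribed daily oral iron at a dose of (3-6mg/kg) elemental iron up to 200mg/day maximum".

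**The concern.** The banding statement covers all three tables, but with 67.5 mg tablets the steps are coarse and several weights appear to fall well outside the stated tolerance. Two bands also share a boundary weight, so at 27 kg the table cannot be followed as written from Day 6.

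Oral iron is the comparator for the primary endpoint. The half-dose start is there to help tolerability and adherence, and section 6.4 measures adherence in this arm. If exposure departs from the stated rule, and does so differently for tablets and liquid, the control treatment is not quite the one described. These are also prescribing instructions for children, so an internal contradiction matters apart from the statistics.

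**Working it through.** **Inputs (sections 6.1.1, 6.1.2 and 4.3).** Tablet 67.5 mg; liquid 6 mg/mL; intended dose 3 mg/kg/day on Days 1–5, then the smaller of 6 mg/kg and 200 mg; tolerance 90–110%.

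**Formula.** Percentage of intended = 100 × (tablets per day × 67.5, or mL × 6 × doses per day) / intended mg per day.

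**Reproducing the stated figure on the liquid tables.** If the 200 mg cap also halves to 100 mg on Days 1–5, every listed weight is within tolerance: 90.9–109.1% for the 12-hourly table and 90.0–109.1% for the 8-hourly table. The Protocol does not state the 100 mg ceiling.

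**Tablets, 20–27 kg (67.5 then 135 mg).** The percentage is the same in both phases:

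- 20 kg: 67.5/60 = 112.5%
- 21 to 25 kg: 107.1% to 90.0%, in range
- 26 kg: 67.5/78 = 86.5%
- 27 kg: 67.5/81 = 83.3%

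**Tablets, 27–32 kg (67.5 then 202.5 mg).**

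| Weight (kg) | Days 1–5 | Day 6 on |
|---|---|---|
| 27 | 83.3% | 125.0% |
| 28 | 80.4% | 120.5% |
| 29 | 77.6% | 116.4% |
| 30 | 75.0% | 112.5% |
| 31 | 72.6% | 108.9% |
| 32 | 70.3% | 105.5% |

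**Tablets, 33 kg and above (135 then 202.5 mg).** Days 1–5 at 33 kg: 135/99 = 136.4%, where a 100 mg ceiling would not bind. Day 6 on: 202.5/198 = 102.3% at 33 kg and 202.5/200 = 101.2% above that, in range.

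**The unstated cap on Days 1–5, at 34 kg and above.**

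- Ceiling of 100 mg: tablets 135/100 = 135%; liquid 96% (12-hourly) or 99% (8-hourly).
- No ceiling at 100 mg: 12-hourly liquid is 96/108 = 88.9% at 36 kg, and 8-hourly liquid is 99/111 = 89.2% at 37 kg; both fall further with weight. Tablets are in range only from 41 kg (135/123 = 109.8%) to 50 kg (135/150 = 90.0%).
- Under either reading the starting dose is 135 mg/day for tablets against 96 or 99 mg/day for liquid.

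**A check that needs no cap.** The starting step is described as half the full dose. In the tablet table it is one half at 20–26 kg, one third at 27–32 kg (1 then 3 tablets) and two thirds at 33 kg and above (2 then 3). In the top liquid bands it is exactly half (8 then 16 mL; 5.5 then 11 mL).

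**Band boundaries.** At 27 kg, from Day 6, one band gives 135 mg (5.0 mg/kg) and the other 202.5 mg (7.5 mg/kg), a 1.5-fold difference; Days 1–5 are 67.5 mg in both. The liquid tables give 156 or 162 mg at that weight from Day 6. A weight between 32 and 33 kg has no tablet band.

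**Daily maximum.** 3 × 67.5 = 202.5 mg, which is 2.5 mg (1.25%) above 200 mg.

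**The case against.** Four points can fairly be made on the other side.

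- **The liquid tables are not a clean benchmark.** A reader might infer that the liquid tables are right and the tablet table wrong. The documents do not support that: the cap is attached only to the full dose, and on a plain 3 mg/kg the liquid tables themselves fail in heavier children. This stands. The tablet failures at 33 kg and below do not depend on the cap.
- **The excess over the maximum is trivial.** Three tablets exceed 200 mg by 1.25%, inside the banding tolerance. This stands; it is a literal inconsistency and not the substance of the point.
- **The effect on total exposure is modest at higher weights.** Taking 28 days of treatment as an illustration at 34 kg and above, tablets total 5 × 135 + 23 × 202.5 = 5,332.5 mg, against 5 × 96 + 23 × 192 = 4,896 mg (12-hourly) or 5 × 99 + 23 × 198 = 5,049 mg (8-hourly). That is about 9% or 6% more. So the table does not show that the comparator as a whole is compromised.
- **Section 4.3 allows a 3–6 mg/kg range.** At 33–45 kg the 135 mg start lies inside it (4.1 to 3.0 mg/kg). The range does not rescue the other cells: at 27–32 kg the start is 2.5 to 2.1 mg/kg, and 202.5 mg at 27 kg is 7.5 mg/kg.

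**Conclusion.** The point holds as an internal contradiction in section 6.1.2. On the Protocol's own figures the fumarate table misses 90–110% at:

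- 20 and 26 kg in both phases;
- 27–32 kg and 33 kg on Days 1–5;
- 27 kg from Day 6 under either band, and 28–30 kg from Day 6.

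The departures run from 70% to 136%. The double assignment at 27 kg is certain. So is the different starting dose of tablets and liquid at 34 kg and above; which form then departs from the stated tolerance cannot be settled until the Days 1–5 cap is. The table is within tolerance at 21–25 kg in both phases and at 31 kg and above from Day 6.

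These results rest only on the stated tablet strength, liquid concentration and intended doses, applied at whole-kilogram weights. The Protocol gives no weight distribution, so the number of participants affected, and any effect on the trial's comparison, cannot be stated. A claim that many children are misdosed would go beyond the documents.

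**What to change.** By amendment, the sponsor, with its pharmacy and haematology advisers, should:

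1. State the intended dose in full, including whether a cap applies on Days 1–5.
2. Reconcile that dose, the 90–110% statement, the 200 mg maximum and the three oral tables with one another.
3. Make the tablet bands non-overlapping and complete, resolving 27 kg and the gap between 32 and 33 kg.
4. Limit the 90–110% statement to the tables and weights where it holds once the cap is settled. Limiting it to the liquid tables now would be premature.

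No view is offered on which dose is right.

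No new data collection is needed. The Appendix E questionnaire already records the dose prescribed and typically taken, separately for liquid and tablets, and the in-patient data sheet in Appendix D records remaining doses. These can be converted to mg/day to summarise exposure by formulation. The cost is one amended section with revised tables and the usual ethics approval of an amendment.

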## 6.2. PREPARATION/HANDLING/STORAGE/ACCOUNTABILITY

### 6.2.1. ACQUISITION AND ACCOUNTABILITY

Oral iron will be dispensed from the Women's and Children's Hospital Pharmacy directly to the patient. We will ask that the patients return any unused tablets or liquid for compliance monitoring.

IV ferric carboxymaltose will be dispensed from the Women's and Children's Hospital Pharmacy to the medical day unit who will prepare and administer the drug in line with the Guidelines for Paediatric Intravenous Drug Administration.

The cost of both preparations will be covered by this project's funding and there will be no out-of-pocket costs for participants in either study arm.

### 6.2.2. FORMULATION, APPEARANCE, PACKAGING, AND LABELLING

Both oral and intravenous iron formulations will be kept in their original packaging with labelling intact.

### 6.2.3. PRODUCT STORAGE AND STABILITY

Oral Iron supplementations (ferrous sulphate liquid and ferrous fumarate tablets) should be stored in a cool, dry place where temperatures stays below 25°C. It should be stored out of the reach of children and animals.

Intravenous ferric carboxymaltose should be stored below 30°C, it should not be refrigerated or frozen. Each vial is single use and any remainder drug should be discarded.

#### 6.2.4. PREPARATION

Oral iron therapy requires no preparation

IV ferric carboxymaltose should be diluted with Sodium Chloride 0.9% as per the following table as per the manufactures guidelines.

Ferinject Volume	Iron Dose	Sodium Chloride 0.9%	Minimum Administration Time
2-4mL	100-200mg	50mL	3 minutes
4-10mL	200-500mg	100mL	6 minutes
10-20mL	500-1000mg	250mL	15 minutes

#### 6.3. MEASURES TO MINIMISE BIAS: RANDOMISATION AND BLINDING

We intend to minimise bias through randomisation using a computer generated randomisation sequence stored in consecutive numbered opaque envelopes. Randomisation will be revealed to the treating team upon opening of the envelope and assignment of the patient to either the control arm (oral iron therapy) or the treatment arm (IV ferric carboxymaltose).

As intravenous cannulation can be a stressful experience for some children and their families we feel it would be unethical to blind the subjects and administer a placebo injection to the patients in the oral therapy arm. Therefore the patients will be unblinded as to their allocation to either the treatment or control arms. We feel this will not significantly bias our results as we will be collecting objective data points (haemoglobin and iron studies).

We will attempt to minimise bias by blinding the outcome assessors and our statistician.

#### 6.4. STUDY INTERVENTION COMPLIANCE

Compliance with the control arm (oral iron therapy) will be assessed two ways.

1. We will ask patients/parents to return any unused iron tablets/liquid to the orthopaedic nurse consultant who will count the remaining tablets/liquid. This will be used to estimate patient medication compliance.
2. Patients/parents will be presented with a compliance questionnaire to survey their overall usage and detail any complaints or side effects. (see Appendix E)

Compliance to the treatment arm (IV ferric carboxymaltose) will be clearly documented in the patient record of attendance at the medical day unit and the patient drug chart.

#### 6.5. CONCOMITANT THERAPY

Not applicable

### 6.5.1. RESCUE MEDICINE

Not applicable

## 7. STUDY INTERVENTION DISCONTINUATION AND PARTICIPANT DISCONTINUATION/WITHDRAWAL

### 7.1. DISCONTINUATION OF STUDY INTERVENTION

Discontinuation from oral or IV iron does not mean discontinuation from the study, and remaining study procedures should be completed as indicated by the study protocol. If a clinically significant finding is identified (including, but not limited to changes from baseline iron studies or haemoglobin) after enrolment, the investigator or qualified designee will determine if any change in participant management is needed. Any new clinically relevant finding will be reported as an adverse event (AE).

The data to be collected at the time of study intervention discontinuation will include the following:

- Oral iron compliance questionnaire
- Documentation of side effects or adverse reactions
- Repeat haemoglobin and iron studies to advise patient of need to continue iron therapy outside of the study

### 7.2. PARTICIPANT DISCONTINUATION/WITHDRAWAL FROM THE STUDY

Participants are free to withdraw from participation in the study at any time upon request. An investigator may discontinue or withdraw a participant from the study for the following reasons:

- Pregnancy
- Significant study intervention non-compliance (refusal to undergo IV iron therapy)
- If any clinical adverse event (AE), laboratory abnormality, or other medical condition or situation occurs such that continued participation in the study would not be in the best interest of the participant
- If the participant meets an exclusion criterion (either newly developed or not previously recognised) that precludes further study participation
- Participant unable to receive oral or IV iron therapy at least 3 weeks preoperatively
- A patient will be discontinued from the study if they do not proceed with surgery during the required timeline from commencing iron therapy.

The reason for participant discontinuation or withdrawal from the study will be recorded on the Iron Deficiency Case Report Form (CRF). Subjects who sign the informed consent form and are randomised but do not receive the study intervention may be replaced. Subjects who sign the informed consent form, and are randomised and receive the study intervention, and subsequently withdraw, or are withdrawn or discontinued from the study, will be replaced.

### 7.3. LOST TO FOLLOW-UP

A participant will be considered lost to follow-up if he or she fails to return for 3 consecutive scheduled visits and is unable to be contacted by the study site staff.

The following actions must be taken if a participant fails to return to the clinic for a required study visit:

- The clinic will attempt to contact the participant and reschedule the missed visit within 1 week and counsel the participant on the importance of maintaining the assigned visit schedule and ascertain if the participant wishes to and/or should continue in the study.
- Before a participant is deemed lost to follow-up, the investigator or designee will make every effort to regain contact with the participant (where possible, 3 telephone calls and, if necessary, a certified letter to the participant's last known mailing address). These contact attempts will be documented in the participant's medical record or study file.
- Should the participant continue to be unreachable, he or she will be considered to have withdrawn from the study with a primary reason of lost to follow-up.

## 8. STUDY ASSESSMENTS AND PROCEDURES

### 8.1. EFFICACY ASSESSMENTS

#### Enrolment visit - 6 weeks (+/-2 weeks) preoperative

The following will be collected:

- Informed Consent
- Full Medical History
- Collection of baseline demographics (age, gender)
- Height and weight
- SRS 30 Questionnaire
- Blood for:
  - Full Blood Exam
  - Iron Studies
  - Electrolytes including Calcium, Magnesium and Phosphate (Order "ELC")
  - Vitamin D Level

#### Group Identification - 5 weeks (+/-2 weeks) preoperative

The investigators will review the results of the screening blood tests (Full Blood Exam and Iron Studies) and determine whether the patient requires preoperative iron therapy.

- Those patients who have normal iron studies will be informed and require no further intervention until their day of surgery
- Those patients who qualify for preoperative iron therapy will be randomised to either the oral or intravenous group.
  - Oral Iron (standard treatment arm)
    - Patients/parents will be informed of their results and group allocation and instructed to collect the oral iron supplements from the Women's and Children's Hospital Pharmacy.
    - Included in will their tablets will be a prescription for weight appropriate dosing, a list of potential side effects and instructions on how to manage frequent side effects as well as a contact number of one of the investigators.
  - Intravenous Iron (treatment arm)
    - Patients/parents will be informed of their results and group allocation and an acceptable appointment time will be found for the patient to present

to the Medical Day unit at the Women's and Children's Hospital to undergo the intravenous iron infusion.

- At their appointment they will be provided with a list of potential side effects and a contact number of one the investigators.

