1.2. SCHEMA

**1.3. SCHEDULE OF ACTIVITIES (SOA)**

Procedures	Enrolment/ Visit 1, Day -42 (+/- 14 days)	Group identification, Day -35 (+/- 14 days)	Study Visit 2, Day -28 (+/- 7 days)	Day Before Surgery Day -1	Day of Surgery Day 0	In hospital Days 1-5	Discharge Day 5 (+/- 2days)	Study Visit 3 Day 21 (+/- 7 days)	Final Study Visit 4 Day 63 (+/- 14 days )
Informed consent	X								
Demographics	X								
Medical history	X								
Baseline screening bloods	X								
Interpretation of bloods		X							
Randomization		X							
Administer study intervention - Intravenous iron therapy (IV arm only)			X						
Administer study intervention - Oral iron therapy (Oral arm only)		X-----X							
Vital signs	X		X		X	X	X		X
Height	X								X
Weight	X								X
SRS 30 Questionnaire	X								X
Full Blood Exam	X				X	X	X	X	X
Iron Studies	X				X				X
Electrolytes (“ELC”)	X				X				X
Vitamin D Level	X								
Surgical data - ASA, spinal levels, blood loss, cell salvage volume					X				
Transfusion volume					X	X	X		
Oral Iron Compliance Questionnaire						X			
Adverse event review and evaluation	X	X-----X							X
Data Entry	X	X	X		X	X	X	X	X

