#### Study Visit - 4 weeks (+/-1 week) preoperative

The patients will undergo their allocation treatment during this time

- Oral Iron
  - Patients will take their oral iron supplementation as prescribed starting from 3-5 weeks preoperatively until the day before surgery
- Intravenous Iron
  - Patients will appointments at the Medical Day unit (MDU) at the Women's and Children's Hospital will be made 3-5 weeks preoperatively.
  - Upon arrival at MDU patients will have a baseline set of vitals collected, they will undergo intravenous cannulation by the orthopaedic resident medical officer, and then receive the intravenous ferric carboxymaltose as described previously.
  - Following the infusion patients will remain in MDU for 45minutes where their vitals will be regularly monitored.

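### Randomisation may fall as late as Day -21, the last day to receive iron under the three-week rule, and only the IV arm then still needs an appointment to be found

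*Protocol*

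**What the plan says.** Protocol Section 8.1 has the steps "Enrolment visit - 6 weeks (+/-2 weeks) preoperative" and "Group Identification - 5 weeks (+/-2 weeks) preoperative". Eligible patients are randomised at the second step, and the Schedule of Activities (Section 1.3) gives the same windows in days. Visit 2, the IV infusion, is at Day -28 +/- 7.

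After allocation the arms follow different routes. Oral patients are "instructed to collect the oral iron supplements from the" hospital pharmacy. For IV patients, "an acceptable appointment time will be found for the patient to present" at the Medical Day Unit.

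Section 7.2 says that an investigator may withdraw a participant for listed reasons, one of which is "Participant unable to receive oral or IV iron therapy at least 3 weeks preoperatively". It adds that consented participants who "are randomised but do not receive the study intervention may be replaced". Section 9.3 describes an intention-to-treat analysis of randomised patients who present for surgery within a timeframe.

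On the oral start, Section 8.1 (4-week visit) has patients taking iron "starting from 3-5 weeks preoperatively until the day before surgery". The synopsis (Section 1.1) describes an oral course of at least 3-5 weeks.

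**The concern.** The last permitted day of randomisation and the last permitted day of treatment coincide. A child can therefore be randomised with no days left, and the effort needed to treat in time differs by arm. One arm has to collect medication. The other needs a booked attendance, cannulation, an infusion and 45 minutes of observation.

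The allocation is open and the withdrawal decision comes after it. If late-randomised IV patients missed the limit more often, and were withdrawn and replaced, the two arms would no longer be losing patients in the same way. That is what randomisation is meant to prevent, and in a trial of 34 a few such cases would be noticeable.

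A smaller, separate matter is that the protocol does not give one clear earliest day for starting oral iron.

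**Working it through.** **Windows, from Sections 1.3, 7.2 and 8.1**
- Enrolment: -42 +/- 14 = Day -56 to -28.
- Group identification and randomisation: -35 +/- 14 = Day -49 to -21. This is 29 permitted days, and Sections 1.3 and 8.1 agree.
- IV infusion: -28 +/- 7 = Day -35 to -21, which agrees with 3-5 weeks in Section 8.1.
- Three-week rule: last compliant day = Day -21.

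**Days left to treat**

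Days left = (days before surgery at randomisation) - 21.

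| Randomised on | Days left |
|---|---|
| Day -35 (nominal) | 35 - 21 = 14 |
| Day -28 | 28 - 21 = 7 |
| Day -24 | 24 - 21 = 3 |
| Day -21 (latest allowed) | 21 - 21 = 0 |

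**Effect of a booking delay**

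The protocol gives no delay, so L days is an assumption. The last workable randomisation day is -(21 + L).
- L = 0: Day -21, 29 of 29 permitted days workable.
- L = 3: Day -24, 26 of 29.
- L = 7: Day -28, 22 of 29.
- L = 14: Day -35, 15 of 29.

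These count calendar days, not patients.

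**Can the late edge be reached?**

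The nominal gap from enrolment to group identification is 42 - 35 = 7 days. If it applied to everyone (an assumption), enrolment on Day -34 would leave 6 days and enrolment on Day -28, the last permitted day, would leave 0. The baseline-results review sheet in Appendix D asks for the surgery date only where it is known, so the time left may not be checkable when the envelope is opened.

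**Weight of one patient**

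1/17 = 5.9% of an arm. This is a unit of scale, not an estimate of bias.

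**Meaning of receiving iron**

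Oral iron runs to the day before surgery, so for that arm the rule can only mean the first dose. For IV iron it is open. Section 6.1.2 caps one dose at 1000 mg or 20 mg/kg and advises two doses a week apart above that. As an illustration, 40 kg with Hb 115 g/L gives 40 x (150 - 115) x 0.24 + 500 = 836 mg, against a cap of 20 x 40 = 800 mg. If the rule meant the full dose, the first infusion would be due by Day -28.

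**Oral start**

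Section 8.1 gives Day -35 to -21, and the five weekly rows of the Appendix E questionnaire fit that. In the text of the Schedule available for review, the oral bar begins in the group identification column, which would allow Day -49 to -21. The two differ only for Day -49 to -36, so by at most 49 - 35 = 14 days.

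**The case against.** The windows do not contradict each other. Randomisation, infusion and the three-week rule all end on the same day, and successive visits often share an outer tolerance. Ordinary flow is well inside it: Sections 4.1 and 5.5 place screening six weeks before surgery, and nominal randomisation at Day -35 leaves 14 days. This stands, and it confines the point to late randomisation.

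The limit names both oral and IV iron, so zero slack applies to both arms, and oral patients must also be told their results and collect the drug. No booking delay, pharmacy delay or count of late randomisations is given. This also stands. The difference between arms is a reasonable inference from the two routes, not a documented fact.

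The harm needs a chain of events: late enrolment, late randomisation, no prompt slot, a decision to withdraw and a decision to replace. The last two are discretionary, and Section 9.3 would keep randomised patients who present for surgery in time. This limits the size but does not remove the risk, because the timeframe that Section 9.3 refers to is said to be in the exclusion criteria and Section 5.2 lists none.

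On the oral start, the Schedule evidence is the position of a bar in a flattened table, the pharmacy instruction does not say when to begin, and the synopsis does not clearly forbid a longer course. That part is an alignment of wording only.

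**Conclusion.** The point holds as a limited design weakness. The protocol permits randomising a child whose only compliant option is treatment on the same day, and the IV route is the harder one to complete that fast. Any resulting withdrawal and replacement could depend on the arm. The number affected is unknown and probably small, and the loss occurs only if the discretionary rule is used.

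A reader might infer that IV patients will be withdrawn more often, or that the comparison is biased by a calculable amount. The documents support neither. They give no booking times and no frequency of late randomisation.

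A reader might also infer that an early oral start undermines the trial. It could lengthen the control course by up to 14 days. If that had any effect it would favour the control arm, which is conservative for a claim of IV superiority.

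The conclusion rests on reading three weeks as 21 days, on the stated windows, and on an infusion slot being harder to obtain the same day than a pharmacy supply.

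**What to change.** 1. In Section 8.1, before the envelope is opened, require a planned surgery date and confirm for every patient that a first dose of either treatment, including an available day-unit slot, can be given by Day -21. If not, do not randomise. Because the check precedes allocation, any exclusion is independent of arm.
2. If a calendar cut-off is preferred, for example randomisation no later than Day -28, move the end of the enrolment window to match, for example from Day -28 to Day -35. Otherwise enrolment and randomisation would share the same zero-slack edge. Day -28 is only an example: it leaves 7 days to book and keeps 22 of the 29 randomisation days.
3. In Section 7.2, state that receiving iron means the first dose.
4. As a minor alignment, make Sections 1.1 and 1.3 follow the Section 8.1 oral start window of Day -35 to -21.

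The cost is wording in Sections 1.1, 1.3, 7.2 and 8.1, and a provisional day-unit slot for each eligible patient, released if the allocation is oral. A few late-screened patients would not be randomised, which matters somewhat in a single-site trial of 34.
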